#### **8.3.5. Clinical Safety Laboratory Assessments**

A central laboratory vendor will be utilized for this study and a laboratory manual will be provided to each site.

See [Appendix 2](#) for the list of clinical safety laboratory tests to be performed and the [SoA](#) for the timing and frequency. All protocol-required laboratory assessments, as defined in [Appendix 2](#), must be conducted in accordance with the laboratory manual and the [SoA](#). Unscheduled clinical laboratory measurements may be obtained at any time during the study to assess any perceived safety issues.

The investigator must review the laboratory report, document this review, and record any clinically significant changes occurring during the study in the AE section of the CRF. Clinically significant abnormal laboratory test findings are those that are not associated with the underlying disease, unless judged by the investigator to be more severe than expected for the participant's condition.

All laboratory tests with values considered clinically significant and abnormal during participation in the study or within 28 to 35 days after the last dose of study intervention should be repeated until the values return to normal or baseline or are no longer considered clinically significant by the investigator or study medical monitor.

If such values do not return to normal/baseline within a period of time judged reasonable by the investigator, the etiology should be identified and the sponsor notified.

See [Appendix 5](#) for suggested actions and follow-up assessments in the event of potential DILI.

See [Appendix 6](#) for instructions for laboratory testing to monitor kidney function and reporting laboratory test abnormalities.

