### **9.3.5. Safety Analyses**

The frequencies of the following postdose safety endpoints will be tabulated by treatment group for the safety analysis set: AEs by intensity; SAEs; AEs related to study intervention; local irritation AEs; laboratory test abnormalities by toxicity grade; and liver function test elevations.

The investigators will determine the intensity of AEs and the relationship of AEs to study intervention. The investigators' terms will be coded using the latest version of the MedDRA available at the start of the study. AEs will be presented by system organ class and preferred term.

Laboratory test results will be graded according to numeric laboratory test criteria in CTCAE if available; otherwise, results will be graded according to numeric laboratory test criteria in DAIDS Table for Grading the Severity of Adult and Pediatric Adverse Events.

Deaths will be listed without regard to onset for the enrolled analysis set.

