## 10.5. Appendix 5: Liver Safety: Suggested Actions and Follow-Up Assessments and Study Intervention Rechallenge Guidelines

### Potential Cases of Drug-Induced Liver Injury

Humans exposed to a drug who show no sign of liver injury (as determined by elevations in transaminases) are termed “tolerators,” while those who show transient liver injury but adapt are termed “adaptors.” In some participants, transaminase elevations are a harbinger of a more serious potential outcome. These participants fail to adapt and therefore are “susceptible” to progressive and serious liver injury, commonly referred to as DILI. Participants who experience a transaminase elevation above  $3 \times \text{ULN}$  should be monitored more frequently to determine if they are “adaptors” or are “susceptible.”

In the majority of DILI cases, elevations in AST and/or ALT precede T bili elevations ( $>2 \times \text{ULN}$ ) by several days or weeks. The increase in T bili typically occurs while AST/ALT is/are still elevated above  $3 \times \text{ULN}$  (ie, AST/ALT and T bili values will be elevated within the same laboratory sample). In rare instances, by the time T bili elevations are detected, AST/ALT values might have decreased. This occurrence is still regarded as a potential DILI. Therefore, abnormal elevations in either AST OR ALT in addition to T bili that meet the criteria outlined below are considered potential DILI (assessed per Hy’s law criteria) cases and should always be considered important medical events, even before all other possible causes of liver injury have been excluded.

The threshold of laboratory abnormalities for a potential DILI case depends on the participant’s individual baseline values and underlying conditions. Participants who present with the following laboratory abnormalities should be evaluated further as potential DILI (Hy’s law) cases to definitively determine the etiology of the abnormal laboratory values:

- Participants with AST/ALT and T bili baseline values within the normal range who subsequently present with AST OR ALT values  $\geq 3 \times \text{ULN}$  AND a T bili value  $\geq 2 \times \text{ULN}$  with no evidence of hemolysis and an alkaline phosphatase value  $< 2 \times \text{ULN}$  or not available.
- For participants with baseline AST **OR** ALT **OR** T bili values above the ULN, the following threshold values are used in the definition mentioned above, as needed, depending on which values are above the ULN at baseline:

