#### 5.2.4. Safety Analysis Periods

Analysis periods	Start date/time	End date/time	Usage
Pre-treatment		Study intervention start date/time	To be used to derive baseline values and to assess the safety endpoints prior to study intervention
On-treatment safety	Study intervention start date/time	Later of (1) Study intervention start date + 9 days and (2) EOT visit date	To be used to assess the safety endpoints during treatment period
Follow-up safety	Later of (1) Study intervention start date + 10 days and (2) EOT visit date + 1 day		To be used to assess the safety endpoints of the follow-up period

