## 6.6.1. Adverse Events

### 6.6.1.1. AE Overview

An AE overview without SOC and PT will present the number of participants evaluable for adverse events, the number of adverse events, the number and percentage of participants with: any AE; mild AE; moderate AE; severe AE; moderate or severe AE; SAE; AE leading to study discontinuation; hepatic-related AE; potential drug abuse AE; cardiovascular AE; suicidality AE; local irritation AE; hypertension AE; Raynaud's phenomenon AE.

An AE overview will be produced by treatment group for each analysis period as defined in Section 5.2.4 using the safety analysis set. All-cause TEAEs (for on-treatment period and follow-up period) and treatment-related TEAEs (for on-treatment period) will be generated separately.

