### 6.6.2.2. Liver Function Test (LFT) Elevations

#### LFT Elevations: Cumulative, Mutually Exclusive, and Composite

The number and percentage of participants with LFT elevations will be summarized for the safety analysis set for pre-treatment period and on-treatment analysis periods, respectively. LFT elevations are based on fold changes above ULN.

LFT elevations include the following categories:

- Cumulative elevations:
  - ALT > 1 x, > 3 x, > 5 x, > 10 x, and > 20 x ULN
  - AST > 1 x, > 3 x, > 5 x, > 10 x, and > 20 x ULN
  - ALT or AST > 1 x, > 3 x, > 5 x, > 10 x, and > 20 x ULN
  - TBL > 1 x, > 1.5 x, and > 2 x ULN
  - ALP > 1 x, > 1.5 x, and > 2 x ULN
- Mutually exclusive elevations:
  - ALT > ULN to  $\leq 3$  x ULN, > 3 x ULN to  $\leq 5$  x ULN, > 5 x ULN to  $\leq 10$  x ULN, > 10 x ULN to  $\leq 20$  x ULN, and > 20 x ULN
  - AST > ULN to  $\leq 3$  x ULN, > 3 x ULN to  $\leq 5$  x ULN, > 5 x ULN to  $\leq 10$  x ULN, > 10 x ULN to  $\leq 20$  x ULN, and > 20 x ULN
  - ALT or AST > ULN to  $\leq 3$  x ULN, > 3 x ULN to  $\leq 5$  x ULN, > 5 x ULN to  $\leq 10$  x ULN, > 10 x ULN to  $\leq 20$  x ULN, and > 20 x ULN
  - TBL > ULN to  $\leq 1.5$  x ULN, > 1.5 x ULN to  $\leq 2$  x ULN, and > 2 x ULN
  - ALP > ULN to  $\leq 1.5$  x ULN, > 1.5 x ULN to  $\leq 2$  x ULN, and > 2 x ULN
- Composite elevations:
  - ALT or AST > 3 x ULN and TBL > 1.5 x ULN
  - ALT or AST > 3 x ULN and TBL > 2 x ULN
  - ALT or AST > 3 x ULN concurrent with TBL > 2 x ULN. Concurrent is defined as elevations on the same collection date.
  - ALT or AST > 3 x ULN concurrent with TBL > 2 x ULN and ALP  $\leq 2$  x ULN. Concurrent is defined as elevations on the same collection date.

- ALT or AST > 3 x ULN concurrent with a selected AE:
  - The following PTs are used to identify selected AEs: nausea, vomiting, decreased appetite, fatigue, and those containing “abdominal pain”.
  - Results are also displayed for each selected AE
  - For a given safety analysis period, an LFT elevation is concurrent with an AE of interest if the imputed AE start date is +/- 7 days inclusive of the LFT collection date; both the LFT collection date and the imputed AE start date must also be in the safety analysis period.

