### eDISH Scatter Plot

An evaluation of drug-induced serious hepatotoxicity (eDISH) scatter plot on-treatment period displays the maximum TBL ratio of value to ULN on the y-axis versus the maximum ALT ratio of value to ULN on the x-axis, where the maxima are in the on-treatment safety analysis period but not necessarily concurrent. Both axes are on the log10 scale with minima of 0.1. Ratios < 0.1x ULN are set to 0.1. Sample sizes in the legend redisplay participants with paired ratios during the on-treatment safety analysis period. A horizontal reference line is placed at 2x ULN, and a vertical reference line is placed at 3x ULN. The lower left quadrant is labeled “Normal Range”, the upper left quadrant is labeled “Hyperbilirubinemia”, the lower right quadrant is labeled “Temple’s Corollary”, and the upper right quadrant is labeled “Possible Hy’s Law Range.” A footnote specifies that “Ratios < 0.1x ULN are set to 0.1”, and is displayed only if  $\geq 1$  participant has a ratio set to 0.1.

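### Liver tests taken after the on-treatment boundary enter none of the planned laboratory displays, so a case that completes late is shown in too low a lab category and is visible only through coded adverse event tables

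*SAP*

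**What the plan says.** SAP 5.2.4 ends the on-treatment safety period at "Later of (1) Study intervention start date + 9 days and (2) EOT visit date". The follow-up safety period starts at "Later of (1) Study intervention start date + 10 days and (2) EOT visit date + 1 day".

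The laboratory displays depend on that boundary:

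- SAP 6.6.2.2: liver test elevations, including the composite ALT/AST-with-bilirubin rows, "will be summarized for the safety analysis set for pre-treatment period and on-treatment analysis periods".
- SAP 6.6.2.2, eDISH plot: maximum ALT against maximum bilirubin, "where the maxima are in the on-treatment safety analysis period but not necessarily concurrent".
- SAP 6.6.2.1: the only table of graded laboratory abnormalities gives the worst on-treatment grade.
- SAP 6.6.2: values and changes are summarised at Baseline and EOT.

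For adverse events, SAP 6.6.1.1 covers all-cause TEAEs in both postdose periods, but "treatment-related TEAEs (for on-treatment period) will be generated separately". SAP 6.6.1.2 and 6.6.1.3 make the same split.

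The protocol is wider. Section 9.3.5 states: "The frequencies of the following postdose safety endpoints will be tabulated by treatment group for the safety analysis set". Its list includes related AEs, laboratory grades and liver test elevations. SAP 2.1 declares no modification of the protocol's analysis plan.

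**The concern.** The boundary falls where late liver data would begin. The schedule of activities has one postdose safety draw, at EOT, so later values come from repeats that the protocol itself asks for. Section 8.3.5 says that clinically significant abnormal values "should be repeated until the values return to normal or baseline" or cease to be clinically significant. Appendix 5 asks for prompt re-evaluation of suspected cases and accepts as potential Hy's law cases those that meet the criteria on repeat testing. It also warns: "In the majority of DILI cases, elevations in AST and/or ALT precede T bili elevations", by days or weeks.

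The value that completes the ALT-bilirubin pair may therefore lie outside every display that applies laboratory criteria. Such a participant would be plotted in the Temple's Corollary quadrant, or even in the normal one, and would be absent from the composite rows. Hepatic events are a named safety topic in both documents, so under-classification matters even if it affects very few participants.

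**Working it through.** **Boundary.** Rule: end = max(dose + 9 days, EOT date). EOT is due within 7 (+2) days, so by day 9. The COVID-19 provision adds 5 days: 9 + 5 = day 14.

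- EOT by day 9: the period ends on day 9. Outside it lie 28 - 9 = 19 of the minimum 28 days of AE collection (68%), or 35 - 9 = 26 of 35 days to the latest Follow-Up Visit (74%).
- EOT on day 14: outside it lie 14 of 28 days (50%) or 21 of 35 days (60%).

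These are shares of calendar time, not of test results. No laboratory draw is scheduled after EOT.

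**Effect on classification.** I applied the eDISH reference lines (ALT >3x ULN, bilirubin >2x ULN) to five assumed courses, first with on-treatment values only and then with all postdose values. Entries are ALT / bilirubin in multiples of ULN.

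| Course | EOT | Repeat | SAP rule | All postdose |
|---|---|---|---|---|
| A | day 7: 4 / 1 | day 9: 5 / 2.5 | Possible Hy's Law | Possible Hy's Law |
| B | day 7: 4 / 1 | day 12: 5 / 2.5 | Temple's Corollary | Possible Hy's Law |
| C | day 7: 2 / 1 | day 14: 6 / 3 | Normal Range | Possible Hy's Law |
| D | day 7: 4 / 2.5 | day 12: 6 / 3 | Possible Hy's Law | Possible Hy's Law |
| E | day 14: 4 / 1 | day 17: 5 / 2.5 | Temple's Corollary | Possible Hy's Law |

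A and D are shown correctly: a repeat by day 9 counts, and so does a pair already complete at EOT. B, C and E are shown too low. If EOT falls on day 9 or later, the boundary is the EOT date itself and every later repeat is excluded. With a single on-treatment sample, the composite rows that do not require concurrency cannot add anything to those that do.

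**Related gaps.**

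- The row for ALT or AST >3x ULN with a selected AE allows 7 days either way but needs both dates in the same period. ALT raised at a day-7 EOT with nausea starting on day 10 is 3 days apart, yet is not counted because day 10 is in follow-up.
- The secondary safety endpoint counts grade 3 or 4 laboratory abnormalities without a time limit, but the only grade table stops at the boundary.
- SAP 3.5.2 pairs EOT with Early Discontinuation for laboratory tests, while 5.2.4 names only the EOT visit. It is unclear whether a later early-discontinuation draw extends the on-treatment period.

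**Illustration of size.** This assumes 630 treated per arm and exactly one late case. The composite row would show 0/630, with an exact 95% upper limit of 1 - 0.025^(1/630) = 0.58%, instead of 1/630 = 0.16%, with an upper limit of 0.88%. The documents give no rate for such events.

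**The case against.** A reader might infer that a late case is never displayed and that the safety tables could report no hepatic signal when the database holds one. The documents do not support that:

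- Protocol Appendix 5 requires potential Hy's law cases to be reported as SAEs, whether or not the work-up is complete.
- SAP 6.6.1.2.3 tabulates follow-up SAEs and TEAEs by arm.
- SAP 6.6.1.1 and 6.6.1.3 count all-cause hepatic-related AEs in follow-up.
- SAP 6.6.1.4 tabulates all-cause and related TEAEs leading to study discontinuation with no stated period, and Protocol 7.2 lists meeting Hy's law criteria among the reasons for discontinuation.

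This stands. What remains is that these tables work from coded terms and do not apply the ALT and bilirubin criteria.

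It is also fair to say that Appendix 5 describes bilirubin as typically rising while transaminases are still raised, in the same sample, and that its lag runs from the transaminase rise, not from EOT. Some pairs will be complete at EOT or by day 9. This limits how often the problem arises but does not remove it.

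A period of at least 9 days is defensible for a single dose with an effective half-life of about 5 to 8 hours (Protocol 2.2.2.1). Protocol section 9 lets the SAP modify the outlined analyses, and the SAP version history openly records dropping related AEs for follow-up. The mismatch with Protocol 9.3.5 is therefore a documentation gap in SAP 2.1, not a breach. None of this argues against an additional display.

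**Conclusion.** The point holds and is minor. Liver tests after the later of dose + 9 days and EOT enter none of the planned elevation tables, composites, eDISH plot or worst-grade table. A case that first meets the criteria on such a repeat is placed in a lower laboratory category and is identifiable only through coded AE tables. Grade 3-4 values after the boundary are uncounted. Related AEs that start after it and do not lead to study discontinuation are in no related-AE table.

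The number of affected participants cannot be estimated, because the documents give neither an event rate nor an expected number of late repeats. The shares of days, the five courses and the 630-per-arm comparison are illustrations. The conclusion assumes that unscheduled repeats are assigned to periods by date, as 5.2.4 reads. Efficacy analyses are untouched.

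**What to change.** 1. In SAP 6.6.2.1, 6.6.2.2 and the eDISH text, add an any-time-postdose version of each display, from study intervention start through the last available value, including unscheduled, early-discontinuation and follow-up repeats. Keep the on-treatment versions beside it.
2. In SAP 6.6.1.1, 6.6.1.2 and 6.6.1.3, also tabulate treatment-related TEAEs for the whole postdose period.
3. In SAP 5.2.4, state how unscheduled and early-discontinuation tests are assigned to periods.
4. If any narrowing from Protocol 9.3.5 is kept, record it in SAP 2.1 with the reason.

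The cost is SAP wording, one extra analysis-period flag and repeat runs of tables already programmed. No new data, visits or participants are needed.

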### eDISH Scatter Plot

An evaluation of drug-induced serious hepatotoxicity (eDISH) scatter plot on-treatment period displays the maximum TBL ratio of value to ULN on the y-axis versus the maximum ALT ratio of value to ULN on the x-axis, where the maxima are in the on-treatment safety analysis period but not necessarily concurrent. Both axes are on the log10 scale with minima of 0.1. Ratios < 0.1x ULN are set to 0.1. Sample sizes in the legend redisplay participants with paired ratios during the on-treatment safety analysis period. A horizontal reference line is placed at 2x ULN, and a vertical reference line is placed at 3x ULN. The lower left quadrant is labeled “Normal Range”, the upper left quadrant is labeled “Hyperbilirubinemia”, the lower right quadrant is labeled “Temple’s Corollary”, and the upper right quadrant is labeled “Possible Hy’s Law Range.” A footnote specifies that “Ratios < 0.1x ULN are set to 0.1”, and is displayed only if  $\geq 1$  participant has a ratio set to 0.1.

### **6.6.3. Vital Signs**

Values and changes from baseline in vital signs will be summarized as continuous variables at Baseline and EOT of the on-treatment safety analysis period by treatment group for the safety analysis set. A separate table of values and changes from baseline in vital signs will be generated for the subgroup of participants with medical history of hypertension.

Vital sign abnormalities during on-treatment period will be summarized by treatment group as the number and percentage of participants in the following categories:

Systolic BP (mm Hg)	min. <90	
Systolic BP (mm Hg) change from baseline	max. decrease $\geq 30$	max. increase $\geq 30$
Diastolic BP (mm Hg)	min. <50	
Diastolic BP (mm Hg) change from baseline	max. decrease $\geq 20$	max. increase $\geq 20$
Pulse rate (bpm)	min. <40	max. >120

A separate table of vital sign abnormalities during on-treatment period for the subgroup of participants with medical history of hypertension will be generated using the following abnormality categories:

Systolic BP (mm Hg)	min. <90	max. >140 max. >160
Systolic BP (mm Hg) change from baseline	max. decrease $\geq 30$	max. increase $\geq 30$
Diastolic BP (mm Hg)	min. <50	max. >90 max. >100
Diastolic BP (mm Hg) change from baseline	max. decrease $\geq 20$	max. increase $\geq 20$
Pulse rate (bpm)	min. <40 min. <60	max. >100 max. >120

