### **2.2.2.1. Clinical Pharmacology**

Based on the completed clinical studies of IN zavegepant, the following observations were made regarding the zavegepant PK properties. Zavegepant is rapidly absorbed ( $T_{\max}$ : 0.54 hr) following a single zavegepant 10 mg IN dose. The effective half-life of zavegepant, which is considered more clinically relevant than elimination half-life as it takes into account the entire plasma concentration-time profile, ranged from approximately 5 to 8 hours across dose levels ranging from 5 to 40 mg IN. Zavegepant exhibits less than dose proportional increases in the exposure following single IN dose administration over the dose range from 1 mg to 40 mg. No evidence of meaningful accumulation was observed across a dose range of 5 to 20 mg zavegepant IN after repeated QD administration.

The results of a DDI study showed that co-administration of sumatriptan with zavegepant IN does not result in a meaningful change in the PK of sumatriptan or of zavegepant. Co-administration of sumatriptan with zavegepant IN does not cause elevations in mean arterial blood pressure or of systolic or diastolic blood pressure greater than those observed with sumatriptan alone. Zavegepant may be co-administered with a triptan without dose frequency modification. Lack of a clinically significant effect on the exposures of EE and LNG following co-administration of zavegepant 20 mg IN and an oral contraceptive support that zavegepant is not a clinically relevant inhibitor of CYP3A4. Zavegepant may be administered with an oral contraceptive without dose frequency adjustment. A 39% increase in the  $C_{max}$  and an approximate two-fold increase in zavegepant AUC was observed in participants with moderate hepatic impairment.

Zavegepant was metabolized by recombinant CYP3A4 and to a lesser extent by recombinant CYP2D6 as shown with in vitro assays, although the overall rate of hepatic metabolism of zavegepant was very low. The human ADME study demonstrated that the primary route of elimination of zavegepant is through biliary elimination, with 84.9% of the total radioactivity recovered in feces following a [ $^{14}C$ ]-zavegepant IV dose, and the contribution of renal clearance to zavegepant elimination is minimal (<12%).

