## 4. STUDY DESIGN

### 4.1. Overall Design

This is a Phase 3, randomized, double-blind, placebo-controlled, multicenter, single-attack, outpatient evaluation of the efficacy and safety of zavegepant versus placebo for the acute treatment of migraine in Asian adults. The study intervention is formulated as zavegepant 10 mg IN or matching placebo. The study intervention will be administered using an unidose nasal spray device containing a single dose of zavegepant or matching placebo. The

PFIZER CONFIDENTIAL

CT02-GSOP Clinical Protocol Template Phase 1 2 3 4 (01 April 2022)

Page 35

090177e19cb4b323\Approved\Approved On: 23-Feb-2023 06:46 (GMT)

participants will be instructed to take their study intervention, as an outpatient, if they have a migraine headache which reaches moderate or severe pain intensity.

The total duration of study participation will be up to approximately 16 weeks. This includes a 3-28 day Screening Phase, a Treatment Phase that can last up to 45 days or until the participant has a migraine headache that reaches moderate or severe pain intensity, followed by an EOT Visit 7 (+2) days after the administration of study intervention and a Follow-Up Visit 28-35 days after the administration of study intervention for safety monitoring.

Approximately 1750 participants will be screened to randomize approximately 1400 participants in a 1:1 ratio between the 2 treatment groups (zavegepant or placebo). Before any study procedures are performed, participants must sign informed consent. After informed consent is signed, participants will be enrolled in the IRT system. The participant's migraine history and medical history will be collected at the Screening Visit. Participants will also undergo all screening procedures as indicated in the SoA. Screening Visit must be completed in person.

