Within 3-28 days from the Screening Visit, participants will return to the site for the Baseline (Randomization) Visit. Participants who meet all eligibility criteria may be randomized at the Baseline Visit. After randomization is completed in the IRT, study intervention will be dispensed to participants to take home for a single attack of moderate or severe pain intensity occurring up to 45 days after the Baseline (Randomization) Visit. The participants will be provided with an eCOA handheld device. The eCOA handheld device may also be referred to as a handheld or an eDiary. Once a participant experiences a migraine headache of moderate to severe intensity, they should record this in the handheld. The handheld will instruct the participant to take study intervention after the initial assessments are completed in the device. The participant will complete assessments for 48 hours after taking study intervention to record efficacy and other quality of life measures, refer to Section 8.2 Efficacy Assessments for additional information. The study personnel **MUST** instruct and train the participant on the proper use of the handheld to **ENSURE** proper understanding and use of the tool, **PRIOR** to the participant leaving the office at Baseline Visit. Baseline Visit must be completed in person. **Participants in this study may be randomized only once. Under NO circumstances may a participant be re-randomized.**

Participants should be encouraged to treat their **FIRST** qualifying migraine attack (moderate or severe pain intensity) that occurs during the Treatment Phase. If participants are unable to treat their first qualifying migraine, refer to Section 6.9.2 Rescue Medication for a list of medications that are allowed during the course of this study.

Participants will return to the site for EOT Visit (after assessments in the handheld are completed) within 7 (+2) days after administration of study intervention. The "+2" day window is included for scheduling purposes only. Every effort should be made to conduct the EOT Visit within the specified window of 7 (+2) days after administration of study intervention. At the EOT Visit, medication compliance and monitoring of safety assessments will be performed as indicated in the SoA. If a participant has **NOT** treated a migraine attack with study intervention within 45 days after randomization, they are still required to complete

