#### 8.3.3.1. Blood Pressure and Pulse Rate

Sitting BP and PR measurements will be assessed with an automated device. Manual techniques will be used only if an automated device is not available. When done manually, PR will be measured in the brachial/radial artery for at least 30 seconds.

BP and PR measurements should be preceded by at least 10 minutes of rest with the participant in a sitting position, in a quiet setting without distractions. The same arm (preferably the dominant arm) will be used throughout the study. Participants should be instructed not to speak during measurements.

Vital signs will be taken before collection for laboratory tests and consist of a single measurement of PR and single BP measurement.

Additional collections of BP and PR will be permitted, as necessary, to ensure appropriate collection of safety data.

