### 9.3.5.1. Electrocardiogram Analyses

Values and changes from baseline for the ECG parameters HR, QTcF, PR interval, and QRS complex will be summarized descriptively by treatment group and time point (ie, baseline and EOT).

The number and percentage of participants with maximum postdose QTcF values and maximum increases from baseline in the categories below will be tabulated by treatment group. The number and percentage of participants with uncorrected QT values >500 ms will also be presented

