#### 6.6.4. Electrocardiograms

Values and changes from baseline in ECG parameters will be summarized as continuous variables by treatment group at Baseline and EOT of the on-treatment safety analysis period for the safety analysis set. Results for overall are only shown at Baseline.

ECG abnormalities during on-treatment period will be summarized by treatment group as the number and percentage of participants in the following categories:

- QTcF (msec): > 450 to 480, > 480 to 500, > 500.
- QTcF interval increase from baseline (msec): > 30 to 60, >60.

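### The all-participant blood-pressure table in SAP 6.6.3 has no absolute high category and rests on one scheduled reading taken well after the single dose

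*SAP*

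**What the plan says.** SAP 6.6.3 introduces the main abnormality table: "Vital sign abnormalities during on-treatment period will be summarized by treatment group as the number and percentage of participants in the following categories". For the whole safety analysis set, the blood-pressure categories are an absolute low (systolic below 90, diastolic below 50 mmHg) and a change in either direction (30 mmHg or more systolic, 20 mmHg or more diastolic). No absolute high pressure is listed. A second table, limited to participants with a medical history of hypertension, adds maxima above 140 and above 160 mmHg systolic and above 90 and above 100 mmHg diastolic.

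For the ECG, Protocol 9.3.5.1 tabulates "The number and percentage of participants with maximum postdose QTcF values and maximum increases from baseline", and SAP 6.6.4 says "ECG abnormalities during on-treatment period will be summarized by treatment group".

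The Schedule of Activities and SAP 3.5.3 and 3.5.4 place one set of vital signs and one ECG after dosing, at EOT or Early Discontinuation. Protocol 8.3.3.1 makes the pressure a single reading per visit, but adds: "Additional collections of BP and PR will be permitted, as necessary". The on-treatment period in SAP 5.2.4 runs from dosing to nine days later, or to the EOT visit if that is later, and is not restricted to scheduled visits.

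The timing of EOT is worded in two ways. Protocol 4.1 first has the treatment phase "followed by an EOT Visit 7 (+2) days after the administration of study intervention", and later has participants return "for EOT Visit (after assessments in the handheld are completed) within 7 (+2) days after administration of study intervention". The Synopsis contains both forms. The Schedule of Activities uses the second, which sets an upper limit and not a target day.

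**The concern.** The drug peaks about half an hour after the spray, and the dose is taken at home. If the only scheduled pressure and ECG come days later, a maximum over the on-treatment period is, for most participants, one late value. Such a table is informative about change that persists to EOT and says little about what happens near peak exposure.

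The readings that could show an acute rise are the unscheduled ones. The all-participant table has no place for a high reading as such: it counts low values and large changes. The high cut-offs are used only where hypertension is already known. Yet a high reading in someone with no such history is the one most likely to be a new finding, and SAP 3.5.1 lists hypertension among the adverse-event groups it singles out.

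At stake is how completely the blood-pressure safety table describes the data, and how far a reader may lean on it. The co-primary and secondary efficacy analyses are not affected.

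**Working it through.** The documents give no figure for the interval in half-lives, so there is nothing to reproduce first.

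**Step 1: how late is the scheduled reading?**

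Inputs:
- Effective half-life of intranasal zavegepant: "ranged from approximately 5 to 8 hours across dose levels ranging from 5 to 40 mg IN" (Protocol 2.2.2.1).
- Tmax after 10 mg intranasally: 0.54 h (same section).
- Earliest EOT under the upper-limit wording: after the handheld assessments, which last 48 h (Protocol 4.1).
- EOT under the target-day wording: day 7 to day 9, that is 168 to 216 h.

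Formula: half-lives elapsed = hours from dose to reading ÷ half-life.

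| EOT reading at | 8 h half-life | 5 h half-life |
|---|---|---|
| 48 h | 48/8 = 6.0 | 48/5 = 9.6 |
| 168 h (day 7) | 168/8 = 21.0 | 168/5 = 33.6 |
| 216 h (day 9) | 216/8 = 27.0 | 216/5 = 43.2 |

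The range is about 6 to 43. The 5-day COVID-19 extension in Protocol 4.1 would allow day 14 (336 h), or 42.0 to 67.2. An Early Discontinuation visit has no stated minimum. Even at the early end, 0.5^6.0 = 1.6% and 0.5^9.6 = 0.13%. These fractions show scale only, because the protocol distinguishes its effective half-life from the elimination half-life. Every EOT value in the table lies far beyond 0.54 h.

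**Step 2: what can pass through the all-participant table uncounted?**

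With readings in whole mmHg, the largest rises that meet no change category are 30 − 1 = 29 systolic and 20 − 1 = 19 diastolic.

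| Assumed predose baseline | Highest uncounted reading |
|---|---|
| 120/80 | 149/99 |
| 140/90 | 169/109 |
| 150/100 | 179/119 |

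The same arithmetic in reverse gives the baselines from which a cut-off can be crossed unseen:
- Above 140 systolic: 141 − 29 = 112 or higher.
- Above 160 systolic: 161 − 29 = 132 or higher.
- Above 90 diastolic: 91 − 19 = 72 or higher.
- Above 100 diastolic: 101 − 19 = 82 or higher.

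The gap is therefore not confined to extreme baselines. The 150/100 row is an illustration. Exclusion criterion 2 (Protocol 5.2) rejects readings above 150 systolic or 100 diastolic at Screening, but SAP 3.5.3 takes the last predose value as baseline, and pressure is measured again at the Baseline Visit. The entry limit does not cap the analysis baseline.

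**Step 3: where else would a high reading appear?**

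It contributes to the continuous summaries if taken at EOT (SAP 6.6.3). It appears as a hypertension adverse event if it meets the adverse-event definition and is reported (Protocol 8.3.3; SAP 6.6.1.3). Neither gives a count of participants above a fixed pressure.

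**The case against.** The strongest reply has four parts.

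- **High pressure is already covered.** Rises of 30/20 mmHg or more, continuous values and changes, and hypertension adverse events are all summarised for the whole safety set. This stands, and it limits the gap to one table. It does not close the gap: dosing is at home with no measurement scheduled near it, so a symptomless rise is unlikely to become an adverse event.
- **Acute effects were studied elsewhere.** Protocol 2.2.2.1 reports no clinically relevant QTc prolongation and gives pressure results with sumatriptan. That is fair context for not scheduling early measurements here. It does not turn this study's late reading into evidence on acute effects.
- **The documents claim no such evidence.** A reader might infer from labels such as on-treatment and maximum postdose that the tables rule out an acute effect. No section says so. On-treatment is a defined period, and the continuous summaries are stated to be at Baseline and EOT. A reader might also take the interval to be at least 21 half-lives. That holds only for an EOT on day 7 or later; the upper-limit wording allows about 6.
- **High cut-offs on a late reading reveal nothing acute and count people already elevated.** The first half is right for scheduled readings, but unscheduled ones can fall in the period. The second half is right, and is why baseline status must be shown beside the maxima.

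Replacing the QTcF maximum with an EOT value would also be a mistake, because it would drop unscheduled ECGs from the table.

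**Conclusion.** The point holds in a limited form. The scheduled EOT pressure and ECG come about 6 to 43 effective half-lives after dosing, depending on how EOT is read, so the abnormality tables cannot assess a transient effect near Tmax unless an unscheduled reading happens to fall there. Separately, the all-participant pressure table omits absolute high categories that the SAP already defines for a subgroup. A rise of up to 29/19 mmHg can cross one or more of those cut-offs without being counted.

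It would go too far to say that no pressure or QTcF signal could ever appear. Unscheduled readings count, larger rises are tabulated for everyone, and a change lasting to EOT would be seen.

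The conclusion assumes that few unscheduled readings are taken close to dosing, which the documents do not quantify, and that the quoted half-life range applies to the 10 mg dose. The missing categories are the substantive defect. The timing is a matter of labelling and interpretation.

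**What to change.** 1. In SAP 6.6.3, apply the existing maxima (above 140 and above 160 systolic, above 90 and above 100 diastolic) to the whole safety analysis set by treatment group, including unscheduled on-treatment readings.
2. Show baseline status against the same cut-offs, so that pre-existing elevation can be told from new elevation.
3. Keep the maximum for postdose QTcF. Footnote the pressure and ECG abnormality tables to say that scheduled readings come from EOT and do not assess acute effects.
4. Reconcile the two EOT wordings across the Synopsis, the Schedule of Activities and Protocol 4.1, and carry the result into SAP 2.3, which repeats both.

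The cost is SAP text and slightly more table output. The categories are already specified for the subgroup and the data are already collected, so no visit or procedure is added. Some participants already elevated at baseline will be counted, which item 2 makes visible.
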